6.1.4 Visit 4 – Follow-up: Month 2 (Week 8 \pm 3 days)

Subjects will arrive in the CRC and will be interviewed by the CRC study personnel regarding change in concomitant medications or changes to their health status since the last visit. A 10 ml blood sample for serology will be drawn and the subject will be released from the CRC.

6.1.5 Visit 5 – Follow-up: Month 3 (Week 12 \pm 3 days)

Procedures will be identical to Visit 4.

	Protocol No.: SciB018
	Version and Date: Version 1.0, March 4, 2015

6.1.6 Visit 6 – Follow-up: Month 4 (Week 16± 3 days)

Procedures will be identical to Visit 4.

6.1.7 Visit 7 – Follow-up: Month 5 (Week 20± 3 days)

Procedures will be identical to Visit 4.

6.1.8 Visit 8 - Third Vaccine Administration: Month 6, (Week 24± 3 days)

The third (last) vaccination will take place 5 months after the second vaccination (Visit 3). The previous injection site will be inspected before the second administration. Procedures will be identical to Visit 2.

6.1.9 Visit 9 – Follow-up: Month 7 (Week 28± 3 days)

Procedures will be identical to Visit 4.

6.1.10 Visit 10 – Follow-up: Month 9 (Week 36± 8 days)

Procedures will be identical to Visit 4.

6.1.11 Visit 11 – Study Termination: Month 12 (Week 48± 8 days)

The following assessments will be performed:

- Physical examination
- Vital signs: (sitting BP, HR, RR, oral temperature)
- 12-lead ECG
- Laboratory safety tests (See Appendix B)
- Serology tests
- AE and concomitant medication recording

The amount of blood drawn in this visit is approximately 23 ml.

The total amount of blood drawn for serology and routine safety laboratory tests will be about 168 ml over a period of 13 months.

6.2 UNSCHEDULED VISIT

An unscheduled visit may be performed at any time during the study at the subject's request or as deemed necessary by the Investigator due to medical considerations. The date and reason for the unscheduled visit will be recorded. AE monitoring and concomitant medication recording will be performed by the Investigator. Other procedures and evaluations will be completed as deemed necessary by the Investigator and may include (but not limited to) safety laboratory tests, ECG, vital signs and physical examination.

6.3 BLOOD SAMPLING FOR IMMUNOGENICITY

6.3.1 Serology Tests

The immunogenicity of the vaccine will be assessed by the anti-HBsAg, anti-preS1 and anti-preS2 antibody levels at each visit, from visit 2 till visit 11, as presented in Appendix A.

	Protocol No.: SciB018
	Version and Date: Version 1.0, March 4, 2015

6.3.2 Blood Sampling and Processing.

Approximately 10 ml of blood will be collected in SST Gel tubes.

Processing and storage of the samples are detailed in the lab manual provided by the Sponsor.

6.3.3 Shipment of Samples to the Bioanalytical Laboratory

Samples will be shipped in a cold pack to the central laboratory on the same day it is drawn from the subject, as detailed in the lab manual provided by the Sponsor.

6.4 SAFETY ASSESSMENTS

Safety assessments will be based on AEs reported by the subject or observed by the Investigator, concomitant medication use, clinically significant changes from baseline of vital signs, ECG, physical examination, and safety laboratory tests (hematology, chemistry, and urinalysis).

6.4.1 Adverse Events (AEs)

AEs will be recorded continuously starting from the signing of the ICF through the Study Termination visit, in those subjects who have been actually dosed.

AEs reported prior to dosing will be recorded in the CRF and considered non-treatment emergent AEs. Any new systemic effect that occurs between scheduled visits should be brought to the attention of the Investigator and recorded in the subject's medical file and in the CRF.

6.4.2 Local reaction at injection site

Local reaction at injection site, based on the FDA Guidance to Industry²⁹ (see grading scale in Appendix C) will be assessed by a study physician on treatment visits.

6.4.3 Vital Signs

Vital signs (sitting systolic and diastolic blood pressure, heart rate, respiratory rate and oral temperature) will be measured after at least 3 minutes rest as per standard practice at the investigational site at the following time points:

- On screening,
- On each treatment visits (Visits 2, 3 and 8): within 60 minutes before vaccination, 60 (\pm 15) minutes after vaccination.
- On Study Termination visit

Changes in vital signs determined by the Investigator to be clinically significant will be noted as an AE on the appropriate CRF and in the subject's file. Such abnormalities will be closely monitored until stabilized or resolved.

6.4.4 Electrocardiogram (ECG)

A 12-lead ECG will be performed at the following time points:

- On screening,
- On Study Termination visit

	Protocol No.: SciB018
	Version and Date: Version 1.0, March 4, 2015

6.4.5 Physical Examination

Complete physical examination will be performed at the following time points:

- On screening,
- On Study Termination visit

Significant changes from baseline examination on screening will be recorded as AEs in the CRF and in the subject's file.

6.4.6 Safety Laboratory Tests

Safety laboratory tests including biochemistry, hematology and urinalysis (see details in Appendix B) will be performed at the following times:

- On screening;
- On each treatment visits (Visits 2, 3 and 8): within 60 minutes before vaccination
- On Study Termination visit (without the screening serology tests)

All safety (chemistry, hematology urinalysis, serology and urine tests will be carried out by AML Laboratories, except urine test for pregnancy which will be performed at the trial site by the CRC staff.

Clinically significant laboratory tests or tests of unknown significance which are outside the normal range may be repeated as clinically indicated until the values return to normal, or until the etiology has been determined and the condition considered stable. Abnormal laboratory test results that are considered to be clinically significant by the investigator will be reported as an AE in the CRF.

7 INVESTIGATIONAL PRODUCTS

7.1 DESCRIPTION OF INVESTIGATIONAL PRODUCT

Sci-B-VacTM is a recombinant Hepatitis B vaccine, produced by SciVac Israel Ltd. It contains the 3 surface antigens of the HBV: HBs, preS1 and preS2 antigens. Each 1ml dose contains sterile 10µg HBs antigen. It is formulated for intramuscular injection supplied in a single use vials containing 1 ml suspension. The components of the investigational vaccine are produced under aseptic conditions and according to the rules of current Good Manufacturing Practice and guidelines applicable to IMPs (investigational medicinal products). The vaccine lot used in this trial will be tested and released by the Quality Assurance Department of the Sponsor.

7.2 PACKAGING AND LABELLING OF INVESTIGATIONAL PRODUCT

All clinical supplies will be provided from the designated commercial batch packed and labeled in compliance with the Good Manufacturing Practices of drugs used in clinical trials and with the Israeli Ministry of Health Guidelines for Clinical Trials in Human Subjects. All study vaccines provided will be appropriately documented.

	Protocol No.: SciB018
	Version and Date: Version 1.0, March 4, 2015

7.3 STUDY DRUG ADMINISTRATION

Sci-B-Vac™ Vaccine will be administered intramuscularly in the deltoid area of the arm, 10 µg/ml, on Month 0, 1 and 6.

Vaccine administration will be documented in the Case Report Forms and on the Drug Administration Records.

Upon loading the syringe by the nurse, with the vaccine, it should be administered to the subjects immediately.

7.4 SHIPMENT OF INVESTIGATIONAL PRODUCT

Prior to study start, study medications will be supplied to the CRC by the Sponsor. It is the responsibility of the Sponsor to ensure the vaccine is kept at 2-8°C during the shipment.

The Sponsor must notify the Investigator/study staff prior to dispatch of drug supplies, with the anticipated date of their arrival, addressed to:

Clinical Trials Unit
TASMC Pharmacy
Tel-Aviv Sourasky Medical Center
[name],
[name]

Shipment of study drug supplies for the study will be accompanied by a shipment form describing the contents of the shipment drug information, acknowledgement of receipt and other appropriate documentation. The shipment form will assist in maintaining current and accurate inventory records.

7.5 RECEIPT AND STORAGE OF INVESTIGATIONAL PRODUCT

All study supplies should arrive at the Pharmacy in sufficient quantity and in time to enable dosing as scheduled.

The investigational product will be accompanied by a shipment form and appropriate documentation.

Vaccines will be stored at the hospital pharmacy in an appropriate locked room until dosing, refrigerated at an average temperature between 2°C to 8°C. During the storage at the pharmacy, the temperature of the refrigerator will be monitored continuously and recorded by a pharmacist or another member of study staff who will record refrigerator temperature log. The Sponsor should be notified for any deviation from the storage conditions. Vaccine vials should never be exposed to freezing temperatures.

The Investigator will issue a prescription, and the vaccines will be picked up from the pharmacy before administration. The vaccines will be transferred from the pharmacy to the CRC in an icebox. The time during which the vaccines will be out of the refrigerator should not exceed 15 min.

	Protocol No.: SciB018
	Version and Date: Version 1.0, March 4, 2015

7.6 ACCOUNTABILITY OF INVESTIGATIONAL PRODUCT

The TASMC pharmacy will be responsible for recording the receipt of all drug supplies and for ensuring the supervision of the storage and allocation of these supplies. When a shipment is received, the pharmacist verifies the quantities received and the accompanying documentation and returns the acknowledgment of receipt to the Sponsor.

Drug administration will be recorded in the source documents, in the CRFs and in the Drug Administration Record form. The latter includes the subject identification, quantity (volume) and date of administration. The containers from which the drug was administered to the subjects will be retained for dose confirmation.

At the end of the study, delivery records of study drug will be reconciled with used / unused stocks and appropriate forms will be filled in, to verify that all used, unused or partially used supplies have been returned and that no study supplies remain in the Investigator's possession.

All unused drug supplies, partially used and empty containers will be returned to the Sponsor or disposed of according to the Sponsor's instructions.

8 STUDY RESTRICTIONS

8.1 CONCOMITANT MEDICATIONS

The following medications are prohibited for use by the subject throughout the study:

- Systemic corticosteroid treatment less than 14 days before first vaccination and throughout the study.
- Immunosuppressant medications (e.g. mycophenolate mofetil, cyclosporine, cyclophosphamide etc.)
- Biological immune-modifying agents (e.g. anti TNF alfa, anti CD20)

8.2 ADDITIONAL RESTRICTIONS

Women of childbearing potential must have a negative serum β -human chorionic gonadotropin (β -HCG) test on screening (and negative consecutive urine tests during the study) and be willing and able to use an acceptable method of birth control (acceptable methods of birth control include: intrauterine devices, oral contraceptive, contraceptive patch, long-acting injectable contraceptive or double-barrier method - condom or diaphragm with spermicide) from the screening visit through the EOS visit, or declare that they are abstaining from sexual intercourse, or be surgically sterile (bilateral tubal ligation, bilateral oophorectomy, or hysterectomy) or post-menopausal.

9 SAFETY AND PHARMACOVIGILANCE

9.1 ADVERSE EVENT DEFINITION

An AE is defined as "Adverse event means any untoward medical occurrence associated with the use of a drug in humans, whether or not considered drug related".

	Protocol No.: SciB018
	Version and Date: Version 1.0, March 4, 2015

An AE (also referred to as an adverse experience) can therefore be any unfavorable and unintended sign (e.g., an abnormal laboratory finding), symptom, or disease temporally associated with the use of a drug, without any judgment about causality or seriousness. An adverse event can arise from any use of the drug (e.g., off-label use, use in combination with another drug) and from any route of administration, formulation, or dose, including an overdose.

An abnormal result of diagnostic procedures including abnormal laboratory findings will be considered an AE if it fulfills one or more of the following:

- Results in subject's withdrawal by the Investigator
- Is associated with a serious adverse event (SAE)
- Is associated with clinical signs or symptoms
- Is considered by the physician to be of clinical significance (a laboratory abnormality that is not clinically significant will not be considered an AE)

A new condition or the worsening of a pre-existing condition will be considered an AE.

An adverse reaction means any adverse event caused by a drug. Adverse reactions are a subset of all suspected adverse reactions for which there is reason to conclude that the drug caused the event.

Suspected adverse reaction is “any adverse event for which there is a reasonable possibility that the drug caused the adverse event.”

AEs do not include the following:

- Stable or intermittent chronic conditions (such as myopia requiring eyeglasses) that are present prior to study entry and recorded in the subject's file and do not worsen during the study
- Medical or surgical procedures (e.g., surgery, endoscopy, tooth extraction, transfusion). The condition that leads to the procedure is an AE if not present at baseline
- Overdose of either study drug or concomitant medication without any signs or symptoms unless the subject is hospitalized for observation
- Hospitalization for elective surgery planned prior to study (situation where an untoward medical occurrence has not occurred)
- Pregnancy alone is not considered an AE. Elective abortions without complications should not be handled as AEs.

All AEs, whether observed by the Investigator or designee or volunteered by or elicited from the subject, should be recorded individually in the CRF. AEs will be recorded from the time a subject has signed the ICF and throughout the study, including the follow up period, in those subjects who have been dosed at least once.

Severity of the AE will be assessed by the investigating physician in accordance with the definitions in Appendix C. An SAE must fulfill the requirements listed in the Section 9.2.

The Investigator will document in his/her opinion the relationship of the AE to the study drug using the criteria outlined in definition of adverse events relationship to study drug (Table 1).

Table 1: Definition of adverse events relationship to study drug

TERM	DEFINITION	CLARIFICATION
Unrelated	In general, this category can be considered applicable to those adverse events, which after careful medical consideration at the time they are evaluated, are judged to be unrelated to the test drug.	An adverse experience may be considered unlikely related if or when (must have two): 
 • It does not follow a reasonable temporal sequence from the administration of the test drug. • It could readily have been produced by the subject’s clinical state, environmental or toxic factors, or other modes of therapy administered to the subject. • It does not follow a known pattern of response to the test drug. • It does not reappear or worsen when the drug is re-administered.
Possibly Related	This category applies to those adverse events for which, after careful medical consideration at the time they are evaluated, a connection with the test drug administration appears unlikely but cannot be ruled out with certainty.	An adverse experience may be considered possibly related if or when (at least two of the following): 
 • It follows a reasonable temporal sequence from administration of the drug. • It could not readily have been produced by the subject’s clinical state, environmental or toxic factors, or other modes of therapy administered to the subject. • It follows a known pattern of response to the test drug.
Probably Related	This category applies to those adverse events which, after careful medical consideration at the time they are evaluated, are felt with a high degree of certainty to be related to the test drug.	An adverse experience may be considered probably related if or when (at least three of the following): 
 • It follows a reasonable temporal sequence from administration of the drug. • It could not be reasonably explained by the known characteristics of the subject’s clinical state, environmental or toxic factors or other modes of therapy administered to the subject. • It disappears or decreases on cessation or reduction in dose. There are important exceptions when an adverse event does not disappear upon discontinuation of the drug, yet drug-relatedness clearly exists. • It follows a known pattern of response to the test drug.

	Protocol No.: SciB018
	Version and Date: Version 1.0, March 4, 2015

Outcomes to Date are classified as follows:

- Recovered – The subject has fully recovered from the adverse event with no residual effects observable
- Recovered with sequelae – The subject has recovered from the adverse event with residual effects observable
- Recovering – the subject status improved but has been recovered
- Ongoing – AE is not recovered
- Fatal
- Unknown

AEs will be coded by Data Management using the using the Medical Dictionary for Regulatory Activities (MedDRA).

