APPENDIX C

TOXICITY GRADING SCALE TABLES

Protocol No.: SciB018

Version and Date: Version 1.0, March 4, 2015

The following tables are based on the " FDA Guidance to Industry: Toxicity Grading Scale for Healthy Adult and Adolescent Volunteers Enrolled in Preventive Vaccine Clinical Trials"²⁹

TABLE 1: GRADING OF LOCAL REACTION

Local Reaction to Injectable Product	Mild (Grade 1)	Moderate (Grade 2)	Severe (Grade 3)	Potentially Life Threatening (Grade 4)
Pain	Does not interfere with activity	Repeated use of non-narcotic pain reliever > 24 hours or interferes with activity	Any use of narcotic pain reliever or prevents daily activity	Emergency room (ER) visit or hospitalization
Tenderness	Mild discomfort to touch	Discomfort with movement	Significant discomfort at rest	ER visit or hospitalization
Erythema/Redness *	2.5 – 5 cm	5.1 – 10 cm	> 10 cm	Necrosis or exfoliative dermatitis
Induration/Swelling **	2.5 – 5 cm and does not interfere with activity	5.1 – 10 cm or interferes with activity	> 10 cm or prevents daily activity	Necrosis

* In addition to grading the measured local reaction at the greatest single diameter, the measurement should be recorded as a continuous variable.

** Induration/Swelling should be evaluated and graded using the functional scale as well as the actual measurement.

Protocol No.: SciB018

Version and Date: Version 1.0, March 4, 2015

TABLE 2: GRADING OF VITAL SIGNS

Vital Signs *	Mild (Grade 1)	Moderate (Grade 2)	Severe (Grade 3)	Potentially Life Threatening (Grade 4)
Fever (°C) ** (°F) **	38.0 – 38.4 100.4 – 101.1	38.5 – 38.9 101.2 – 102.0	39.0 – 40 102.1 – 104	> 40 > 104
Tachycardia - beats per minute	101 – 115	116 – 130	> 130	ER visit or hospitalization for arrhythmia
Bradycardia - beats per minute***	50 – 54	45 – 49	< 45	ER visit or hospitalization for arrhythmia
Hypertension (systolic) - mm Hg	141 – 150	151 – 155	> 155	ER visit or hospitalization for malignant hypertension
Hypertension (diastolic) - mm Hg	91 – 95	96 – 100	> 100	ER visit or hospitalization for malignant hypertension
Hypotension (systolic) – mm Hg	85 – 89	80 – 84	< 80	ER visit or hospitalization for hypotensive shock
Respiratory Rate – breaths per minute	17 – 20	21 – 25	> 25	Intubation

* Subject should be at rest for all vital sign measurements.

** Oral temperature; no recent hot or cold beverages or smoking.

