*** When resting heart rate is between 60 – 100 beats per minute. Use clinical judgment when characterizing bradycardia among some healthy subject populations, for example, conditioned athletes.

Protocol No.: SciB018

Version and Date: Version 1.0, March 4, 2015

TABLE 3: GRADING OF SYSTEMIC SYMPTOMS

Systemic (General)	Mild (Grade 1)	Moderate (Grade 2)	Severe (Grade 3)	Potentially Life Threatening (Grade 4)
Nausea/vomiting	No interference with activity or 1 – 2 episodes/24 hours	Some interference with activity or > 2 episodes/24 hours	Prevents daily activity, requires outpatient IV hydration	ER visit or hospitalization for hypotensive shock
Diarrhea	2 – 3 loose stools or < 400 gms/24 hours	4 – 5 stools or 400 – 800 gms/24 hours	6 or more watery stools or > 800gms/24 hours or requires outpatient IV hydration	ER visit or hospitalization
Headache	No interference with activity	Repeated use of non-narcotic pain reliever > 24 hours or some interference with activity	Significant; any use of narcotic pain reliever or prevents daily activity	ER visit or hospitalization
Fatigue	No interference with activity	Some interference with activity	Significant; prevents daily activity	ER visit or hospitalization
Myalgia	No interference with activity	Some interference with activity	Significant; prevents daily activity	ER visit or hospitalization
Illness or clinical adverse event (as defined according to applicable regulations)	No interference with activity	Some interference with activity not requiring medical intervention	Prevents daily activity and requires medical intervention	ER visit or hospitalization

Protocol No.: SciB018

Version and Date: Version 1.0, March 4, 2015

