4.7.3 Laboratory Test Results

Analyses of safety laboratory data will be performed in the following manner:

- Descriptive statistics of quantitative tests results and changes from baseline by scheduled visit.
- Quantitative laboratory measurements will be categorized with reference to the normal ranges as Low, Normal or High. Incidence tables of laboratory results categories will be presented by visit.
- Incidence tables of CS lab values defined by the PI as well as the individual subject listing will also be provided.
- Box-Plots of laboratory measurements from first study dose and afterwards by scheduled visit will be provided by request for specific parameters.

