5. APPENDIX I: TABLES TO BE INCLUDED IN THE STATISTICAL REPORT

Table number	Table Title
14.1	Demographic and Baseline Data
14.1-1.1	Disposition of subjects
14.1-1.2	Primary reason for early discontinuation
14.1-2.1	Analysis population
14.1-3.1	Demographic and Baseline data, ITT
14.1-4	Medical History, ITT
14.1-5	Baseline Physical Examination, ITT
14.1-6	Any Concomitant Medication, ITT
14.1-7	Any Concomitant Non-drug Medication, ITT
14.1.2	Exposure to Sci-B-Vac injection
14.1.2.1	Sci-B-Vac injection, ITT
14.2	Efficacy Analysis
14.2-1	Seroprotection rate (SPR) by Month, mITT
14.2-2	Seroprotection rate (SPR) by Month, FT (for first IA mITT who completed month 7 will be presented)
14.2-3	Secondary Endpoint Analysis: Percentage of Subjects with Anti-HBs \geq 100 mIU/ml by Month, mITT
14.2-4	Secondary Endpoint Analysis: Percentage of Subjects with Anti-HBs \geq 100 mIU/ml) by Month, FT (for first IA mITT who completed month 7 will be presented)
14.2-5	Geometric means of anti-HBs antibody titers by month, mITT
14.2-6	Geometric means of anti-HBs antibody titers by month, FT (for first IA mITT who completed month 7 will be presented)
14.2-7	Frequency of gender by responders (SPR) (at month 4 for first IA)
14.2-8	Frequency of age categories by responders (SPR) (at month 4 for first IA)
14.2-9	Frequency of Responders (SPR) by Smoking status and month (month 4 for IA)
14.2-10	Frequency of Responders (SPR) by BMI categories and month (at month 4 for first IA)
14.2-11	Geometric means of anti-HBs antibody titers by month and Gender
14.2-12	Geometric means of anti-HBs antibody titers by month and age categories
14.2-13	Geometric means of anti-HBs antibody titers by month and Smoking status
14.2-14	Geometric means of anti-HBsAg antibody titers by month and BMI categories
14.2-15	Serologic Markers for Hepatitis B Infection, ITT
14.3	Safety Data
14.3.1	Adverse Events
14.3.1	Summary Incidence of TEAE (Treatment Emergent Adverse Events), ITT
14.3.1-1	Summary of Adverse Events by SOC and PT, ITT

Table number	Table Title
14.3.1-2	Summary of Adverse Events by SOC and PT and Severity, ITT
14.3.1-3	Summary of Adverse Events by SOC and PT and Relation to study drug, ITT
14.3.1-4	Summary of Serious Adverse Events by SOC and PT, ITT
14.3.2	Listing of SAEs (if applicable)
14.3.2-1	Listing of Serious Adverse Events
14.3.4	Abnormal Laboratory Results
14.3.4-1	Incidence of Hematology Abnormal Clinically Significant Results
14.3.4-2	Out of Range Hematology Results

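### Appendix C sets the severity of adverse events but has no laboratory scale, so a markedly abnormal, symptom-free laboratory result can be graded Mild or fit no grade

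*Protocol*

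**What the plan says.** Protocol 9.1, with the same sentence in versions 1.0 and 2.0, sets the severity rule: "Severity of the AE will be assessed by the investigating physician in accordance with the definitions in Appendix C".

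Laboratory findings fall under that rule. Protocol 6.4.6 says: "Abnormal laboratory test results that are considered to be clinically significant by the investigator will be reported as an AE in the CRF". Section 9.1 also counts an abnormal laboratory finding as an adverse event when the physician considers it clinically significant. The synopsis, under Safety Assessments, makes the severity of adverse events part of the primary safety endpoint and expressly includes clinically significant laboratory abnormalities.

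Appendix C, in version 1.0, has three tables:
- "TABLE 1: GRADING OF LOCAL REACTION"
- "TABLE 2: GRADING OF VITAL SIGNS"
- "TABLE 3: GRADING OF SYSTEMIC SYMPTOMS"

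The last row of the third table is the only general one: "Illness or clinical adverse event (as defined according to applicable regulations").

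On the analysis side, SAP Appendix I lists Table 14.3.1-2, "Summary of Adverse Events by SOC and PT and Severity, ITT". For laboratory values, SAP 4.7.3 says: "Quantitative laboratory measurements will be categorized with reference to the normal ranges as Low, Normal or High". It also plans descriptive statistics, changes from baseline, and incidence tables and a listing of results that the investigator judges clinically significant. It plans no toxicity grades.

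**The concern.** A laboratory adverse event needs a severity grade, and the standard that must supply it contains no laboratory value. The general row grades by what happened to the subject's activity or care, not by how abnormal the result was. Many laboratory changes cause no symptoms, so this row is a poor measure of them.

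The severity column of Table 14.3.1-2 is at stake. For laboratory events it could show Mild where the value is far from the reference limit, and two investigators could grade the same result differently. In an open-label, single-arm study the investigator decides both whether a result is an adverse event and how severe it is, so an explicit scale matters more. The immunogenicity conclusion is not touched.

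**Working it through.** No power, alpha or rate is involved. The check is to read Appendix C row by row, apply it to a laboratory event, and see whether the SAP supplies what is missing.

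**1. Which row could apply.** Tables 1 and 2 cover local reactions and vital signs. The named rows of Table 3 are nausea/vomiting, diarrhoea, headache, fatigue and myalgia. That leaves the general illness row, although neither document says that it covers laboratory findings.

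**2. What that row gives for a symptom-free laboratory event.**
- *No treatment, no emergency-room visit or admission.* Activity is unaffected, which is the Grade 1 criterion. The grade is 1 at any value.
- *Treated as an outpatient, activity unaffected.* Grade 1 fits on activity but is silent on treatment. Grade 2 needs some loss of activity and no treatment. Grade 3 needs both prevented activity and treatment. No grade fits cleanly.
- *Emergency-room visit or admission.* Grade 4, with or without symptoms.

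Two very different values can therefore share a grade, and the same value can be Grade 1 or Grade 4 depending on where the subject was seen.

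**3. Contrast with vital signs.** Table 2 grades by number: a systolic pressure above 155 mm Hg is Grade 3 even without symptoms. SAP 4.7.2 reproduces that scale, and Table 14.3.12 tabulates the grades by visit. Laboratory values have no counterpart.

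**4. Does Amendment 1 close the gap?** Version 2.0 added pointers to Table 3 for systemic symptoms (6.4.1), Table 1 for local reactions (6.4.2) and Table 2 for vital signs (6.4.3). Its laboratory section (6.4.6) points to no grading table. The version 2.0 Appendix C is not in the supplied text. From the contents pages, Appendix C runs from page 51 to 54 in version 1.0 (Appendix D starts on 55) and from 52 to 55 in version 2.0 (Appendix D starts on 56). That is four pages in each, so an added laboratory table is unlikely, though not excluded.

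**5. Does the SAP close it?** Low/Normal/High puts a value just outside the limit in the same class as an extreme one. Protocol 10.9.3 had planned incidence tables of potentially clinically significant values, without defining limits, and a shift analysis. SAP 4.7.3 uses investigator-defined clinical significance instead and names no shift table. However, SAP 3.2 lists all measured variables individually, SAP 3.3 gives minimum and maximum, and Tables 14.3.5 to 14.3.10 give results and changes from baseline by visit. Tables 14.3.4-1, -3 and -5 count clinically significant results. The size of an abnormality can be seen there; its severity grade cannot.

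**6. Extent.** The Appendix B interim and termination list has 14 chemistry, 8 haematology and 11 urinalysis items: 14 + 8 + 11 = 33, none with a severity scale. Chemistry and haematology, where a value-based scale is proposed, make 14 + 8 = 22.

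**The case against.** A reader might infer that every symptom-free laboratory event, however extreme, will be graded Mild. The documents do not support that. No sentence assigns Mild to such events, the general row is not stated to cover them, an emergency-room visit or admission gives Grade 4, and outpatient treatment without lost activity has no clear grade. A reader might also infer that the SAP hides how large an abnormality was. It does not, for the reasons in step 5 of the working.

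Three further points limit the effect:
- Seriousness is judged separately from severity. Protocol 9.2 names blood dyscrasias that do not lead to admission among its examples of events normally regarded as serious. Serious events go to the sponsor within 24 hours and appear in Table 14.3.1-4 and Listing 14.3.2-1.
- Subjects are healthy adults with no clinically significant laboratory abnormality at screening. Scheduled safety samples after the first dose fall only at Months 1, 6 and 12, and no between-group comparison rests on the grade.
- The Appendix C that can be read belongs to version 1.0. The SAP enrols up to 92 subjects against 84 in protocol version 2.0, and its history mentions protocol changes, so a later amendment may exist.

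These points stand and limit the size of the problem. They do not supply a severity definition. It can also be said that one sentence on how laboratory events are graded would be enough. Such a sentence would remove the ambiguity, but if it pointed to the general row the grade would still ignore the value.

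**Conclusion.** The point holds in this form: the prescribed severity standard has no laboratory scale, so a named component of the primary safety endpoint lacks a value-based definition for laboratory events. If the general row is used, an untreated, symptom-free result reads as Grade 1 at any value, and an outpatient-treated one without lost activity fits no grade cleanly. Table 14.3.1-2 can then understate severity or report it inconsistently. Understatement is possible, not certain, and the number of events affected cannot be estimated from the documents.

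This rests on two assumptions: that the general row is the one investigators would use, and that the Appendix C in force resembles version 1.0. The page counts, the version 2.0 pointers to Tables 1 to 3 only, and a SAP that takes vital-sign grades from Appendix C but no laboratory grades all favour the second. The gap should be closed, but it bears on safety reporting only.

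**What to change.** - **Appendix C:** add a table that grades the 22 chemistry and haematology analytes in the Appendix B interim and termination list by value, taken from a recognised vaccine-trial toxicity scale or set against the laboratory's reference limits. Leave urinalysis out.
- **Protocol 9.1:** name that table as the severity standard for laboratory adverse events. First confirm that the Appendix C in force does not already contain one.
- **SAP 4.7.3:** grade post-dose values by program and tabulate the worst post-dose grade per subject beside the Low/Normal/High counts.

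The cost is one appendix table and some programming on data already collected. The downside for the sponsor is that some laboratory events will be reported above Grade 1.
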